7.7. Changes From Protocol-Specified Safety Analyses

There are no deviations from the protocol-specified safety analyses.

8. PHARMACOKINETIC (PK) ANALYSES

8.1. PK Sample Collection

A single predose PK blood sample (Sparse PK Sampling) will be collected at Week 1, 2, 4, 8, and 12 in BD Phase for all subjects.

PPD

A population PK model will be developed to characterize the PK of GS-9674 and its metabolites (as applicable). Data from this study (single PK PPD) will be combined with data from other studies in a meta-population analysis using nonlinear mixed-effects modeling techniques. Details of the population PK analysis will be provided in a separate population PK analysis plan.

8.2. PK Analyses Related to Intensive PK Sampling

PPD

8.2.1. Estimation of PK Parameters

PK parameters will be estimated using Phoenix WinNonlin® software using standard noncompartmental methods. The linear up/log down rule will be used in conjunction with the appropriate noncompartmental model, with input values for dose level, dosing time, plasma concentration, and corresponding real-time values, based on drug dosing times whenever possible.

All predose sample times before time-zero will be converted to 0. Predose samples may also be used as $t=24$ hr postdose samples for the purposes of PK parameter generation, as appropriate.

For area under the curve (AUC), samples BLQ of the bioanalytical assays occurring prior to the achievement of the first quantifiable concentration will be assigned a concentration value of 0 to prevent overestimation of the initial AUC. Samples that are BLQ at all other time points will be treated as missing data in WinNonlin. The nominal time point for a key event or dosing interval (τ) may be used to permit direct calculation of AUC over specific time intervals. The appropriateness of this approach will be assessed by the PK scientist on a profile-by-profile basis.

Pharmacokinetic parameters such as AUC_{tau} , λ_z and $t_{1/2}$ are dependent on an accurate estimation of the terminal elimination phase of drug. The appropriateness of calculating these parameters will be evaluated upon inspection of PK data on a profile-by-profile basis by the PK scientist.

8.2.2. PK Parameters

PPD

PPD

The analytes and parameters presented in **Table 8-2** will be used to evaluate the PK objectives of the study. The PK parameters to be estimated in this study are listed and defined in the PK Abbreviations section.

Table 8-2. PK Parameters for Each Analyte

[figure not shown]
Analyte	Parameters
GS-9674	AUC _{last} , AUC _{tau} , C _{max} , T _{max} , C _{last} , T _{last} , C _{tau} , λz, CLss/F, and t _{1/2}
GS-716070	AUC _{last} , AUC _{tau} , C _{max} , T _{max} , C _{last} , T _{last} , C _{tau} , λz, and t _{1/2}

Individual subject concentration data and individual subject PK parameters for GS-9674 and its metabolites (as appropriate), will be listed and summarized using descriptive statistics by treatment. Summary statistics (n, mean, SD, coefficient of variation [%CV], median, min, max, Q1, and Q3) will be presented for both individual subject concentration data by time point and individual subject PK parameters by treatment. Moreover, the geometric mean, 95% CI, and the mean and SD of the natural log-transformed values will be presented for individual subject PK parameter data.

Individual concentration data listings and summaries will include all subjects with concentration data. The sample size for each time point will be based on the number of subjects with nonmissing concentration data at that time point. The number of subjects with concentration BLQ will be presented for each time point. For summary statistics, BLQ values will be treated as 0 at predose and one-half of the lower limit of quantitation (LLOQ) for postdose time points.

Individual PK parameter data listings and summaries will include all subjects for whom PK parameter(s) can be derived. The sample size for each PK parameter will be based on the number of subjects with nonmissing data for that PK parameter.

PPD

The following listings will be provided:

- PK sampling details by subject including actual dosing time, actual draw time, calculated time postdose of sample collection, differences in scheduled and actual draw times, sample age, and sample concentration
- Individual data on determination of plasma half-life and corresponding correlation coefficient

8.3. PK Analyses Related to Sparse PK Sampling

Single PK concentration data along with the actual collection time and dosing time, and calculated time postdose of sample collection will be included in the corresponding PK data listing described in Section 8.2.2.

10. SOFTWARE

SAS® Software Version 9.4. SAS Institute Inc., Cary, NC, USA.

11. SAP REVISION

Revision (DD MMM YYYY)	Date	Section	Summary of Revision	Reason for Revision

12. APPENDICES

- Appendix 1. Study Procedures Table
- Appendix 2. CTCAE Grading Scale for Severity of Adverse Events and Laboratory Abnormalities
- Appendix 3. Programming Specifications

Appendix 1. Study Procedures Table

		Blinded Study Phase Treatment Weeks (± 3 days)							OLE Weeks (± 3 days weeks 1-12 and ± 5 days weeks 24-96)		
		Screening ^a	Baseline (Day 1)	Week 1	Week 2	Week 4	Week 8	Week 12 /ET ^b	Blinded Study Phase follow-up visit ^c (± 5 days)	OLE Baseline/Day 1, Weeks 1, 2, 4, 8, 12, 24, 36, 48, 60, 72, 84, 96/ET ^b	OLE follow-up ^d
Subject Fasting		X	X	X	X	X	X			X	
Written Informed Consent ^e	X										
Review Inclusion/Exclusion Criteria	X	X									
Medical History	X										
Partial Mayo Score ^f	X	X	X	X	X	X	X	X	X	X	
Pruritus VAS &5D-Itch ^g		X	X	X	X	X	X	X	X	X	
QoL SF-36, PSC-PRO & PBC-40 ^g		X					X	X	X		
Symptom-directed PE ^h	X	X	X	X	X	X	X	X	X	X	
Vital Signs ⁱ	X	X	X	X	X	X	X	X	X	X	
Height and weight ^j	X	X	X	X	X	X	X	X	X	X	
Chemistry	X	X	X	X	X	X	X	X	X	X	
Hematology	X	X	X	X	X	X	X	X	X	X	
Coagulation Panel	X	X	X	X	X	X	X	X	X	X	

		Blinded Study Phase Treatment Weeks (± 3 days)							OLE Weeks (± 3 days weeks 1-12 and ± 5 days weeks 24-96)	
		Screening ^a	Baseline (Day 1)	Week 1	Week 2	Week 4	Week 8	Week 12 /ET ^b	Blinded Study Phase follow-up visit ^c (± 5 days)	OLE Baseline/Day 1, Weeks 1, 2, 4, 8, 12, 24, 36, 48, 60, 72, 84, 96/ET ^b
Cirrhosis Assessments	X									
Lipid Profile		X	X		X	X	X	X	X	X
C-Peptide, Hemoglobin A1C and Insulin		X					X			
Blood Biomarkers ^k for Biomarkers ^k	X	X	X		X		X	X	X	
Single PK and PD Sampling		X ¹	X	X	X	X	X			
HIV-1, HBV and HCV Serology	X									
Pregnancy Test ^m	X	X	X		X	X	X	X	X	X
Serum FSH ⁿ	X									
PPD										
12- lead ECGs		X					X			
Fibroscan ^p		X					X			
MRE ^q		X							X	
MRCP ^r		X							X	

		Blinded Study Phase Treatment Weeks (± 3 days)							OLE Weeks (± 3 days weeks 1-12 and ± 5 days weeks 24-96)	
		Screening ^a	Baseline (Day 1)	Week 1	Week 2	Week 4	Week 8	Week 12 /ET ^b	Blinded Study Phase follow-up visit ^c (± 5 days)	OLE Baseline/Day 1, Weeks 1, 2, 4, 8, 12, 24, 36, 48, 60, 72, 84, 96/ET ^b
Urine drug screening	X									
Urine collection (Biomarkers) ^e		X	X		X		X	X	X	
Stool collection (Biomarkers) ^e		X					X	X	X	
PPD										
Dispense GS-9674/PTM GS-9674 ^v		X			X	X			X	
Concomitant Medications	X	X	X	X	X	X	X	X	X	X
Adverse Events	X	X	X	X	X	X	X	X	X	X
Take GS-9674/PTM GS-9674 Tablets		X – Daily (Baseline/ Day 1 to Week 12) ^w							X-Daily (OLE Baseline/ Day 1 to Week 96)	

a The visit window may be extended under special circumstances with explicit approval of the Medical Monitor. Subjects who fail to meet eligibility criteria due to an abnormal laboratory result may undergo re-testing of the abnormal analyte during the screening window. This will be done at the discretion of the investigator and also with prior approval of the Medical Monitor.

b Blinded Study Phase subjects discontinuing the study at any time for any reason (Early Termination – ET) should complete the procedures listed for the Week 12/ Visit AND the follow-up visit. OLE Phase subjects discontinuing the study at any time for any reason (Early Termination – ET) should complete the procedures listed for the Week 96/ Visit AND the follow-up visit if possible.

c After completing 12 weeks of treatment in the Blinded Study Phase, subjects will return for the follow-up visit 4 weeks post the last dose of the study drug and at that time they can begin their OLE Phase. Follow-up visit for Blinded Study Phase and Baseline/Day 1 OLE visit can occur on the same day if convenient. If OLE Baseline/Day 1 and Blinded study follow-Up visit is on the same day subjects should only complete OLE Baseline/Day 1 assessments.

d Follow-up visit should be completed during the Blinded Study Phase as well as the OLE Phase.

e Obtain written informed consent before initiation of any screening procedure.

- f Phone follow-up every 4 weeks after OLE Week 12, (OLE Week 16, 20, 28, 32, 40, 44, 52, 56, 64, 68, 76, 80, 88 and 92).
- g QoL questionnaires and Pruritus assessments should be completed prior to any study procedures being performed and prior to the subject seeing a health care provider. Refer to the Study Reference Binder for guidance on QoL questionnaire administration. During OLE, QoL questionnaires are required at OLE Baseline/Day 1, Weeks 4, 12 and every 12 weeks thereafter.
- h Complete PE at screening and symptom-directed PE for other visits. The focus of a symptom-driven physical examination will be determined by the investigator based on subject complaint.
- i Vital signs include (heart rate, systolic and diastolic blood pressure, respiratory rate, and body temperature)
- j Height should be collected at Screening and Baseline/Day 1 only. Weight should be collected at all visits. Refer to the Study Reference Binder for specific instructions on how weight should be measured.
- k Biomarker analyses include, but are not limited to, the tests listed in Section 6.12.1 of the protocol. Some of the blood collected for biomarkers may be stored for future testing.
- l PD sampling only at Baseline/Day 1.
- m Females of childbearing potential only (see Appendix 4 of the protocol). Serum pregnancy tests at Screening. Urine pregnancy test at all other visits, except Blinded Study Phase Week 2 and OLE Weeks 1, and 2.
- n Only required for some female subjects – see Appendix 4 of the protocol.
- PPD
- p Subject should be in fasted state for FibroScan® collection. Refer to the study reference binder for further details. If FibroScan® is not available at a site the test may be omitted.
- q Should be in a fasted state for MRE scan. Refer to study reference binder for further details. If MRE is not available at a site the test may be omitted. MRE scan should be performed at Blinded Study Phase Baseline/Day 1 and OLE Weeks 48 and 96.
- r MRCP is to be performed at Blinded Study Phase Baseline/Day 1 and OLE Weeks 48 and 96. Refer to study reference binder for further details.
- s Urine Biomarker sample collection at Blinded Study Phase Baseline/Day 1, week 1, weeks 4, 12 and at the Follow up and Early term visits. Urine Biomarker sample collection during OLE at OLE Baseline/Day 1, Weeks 24, 48, 72 and 96 only.
- t Stool sample collection at Blinded Study Phase Baseline/Day 1, Week 12 and at the Follow up and Early term visits. Stool sample collection during OLE at OLE Baseline/Day 1, Week 48 and Week 96 visit
- PPD
- v Study drug will be assigned via the IWRS system every 4 weeks from Baseline/Day 1 through Week 8 in Blinded Study Phase and at OLE Baseline/Day 1, Weeks 1, 4, 8 12 and every 12 weeks thereafter.
- w Subjects to self-administer the study drug at the investigative site at the conclusion of the Blinded Study Phase Baseline/Day 1 and Week 12 visit.

**Appendix 2. CTCAE Grading Scale for Severity of Adverse Events and
Laboratory Abnormalities**

http://evs.nci.nih.gov/ftp1/CTCAE/CTCAE_4.03_2010-06-14_QuickReference_8.5x11.pdf

Appendix 3. Programming Specifications

FibroSURE/FibroTest® Calculation:

Step-1 formula	$f5 = 4.467 \times \text{Log}[\alpha_2\text{-macroglobulin(g/L)}] - 1.357 \times \text{Log}[\text{Haptoglobin (g/L)}] + 1.017 \times \text{Log}[\text{GGT(U/L)}] + 0.028 \times [\text{Age (year)}] + 1.737 \times \text{Log} [\text{Total Bilirubin (umol/L)}] - 1.184 \times [\text{ApoA1 (g/L)}] + 0.301 \times \text{Sex (female = 0, male = 1)} - 5.540$
Step-2 formula	$\text{FibroSURE/FibroTest}^{\circledR} \text{ Score} = 1/(1+\text{exp}^{(-f5)})$
Note	
• In the formula, SI value and units should be applied.• The Log function in the formula is with base 10.• FibroSURE/FibroTest® score should be calculated from the parameters from the same blood draw• Age is when the blood draw was taken

For subject with Gilbert's syndrome or hemolysis according to the medical history page at screening, the FibroSURE/FibroTest® score will be calculated using Direct Bilirubin instead of Total Bilirubin in above formula throughout the study.

HOMA-IR Calculation:

HOMA-IR = fasting glucose (mg/dL) \times fasting insulin (muIU/mL) / 405. Keep 2 decimal places. The lab parameters need to be measured from the same blood draw.

Pooled Cohort Risk Score:

No.	Parameters	Coefficient			
		Female		Male	
		White or Other	African America	White or Other	African America
1	ln Age (y)	-29.799	17.114	12.344	2.469
2	ln Age, Squared	4.884	N/A	N/A	N/A
3	ln Total Cholesterol (mg/dL)	13.540	0.940	11.853	0.302
4	ln Age × ln Total Cholesterol	-3.114	N/A	-2.664	N/A
5	ln HDL-C (mg/dL)	-13.578	-18.920	-7.990	-0.307
6	ln Age × ln HDL-C	3.149	4.475	1.769	N/A
7	ln Treated Systolic BP (mm Hg)	2.019	29.291	1.797	1.916
8	ln Age × ln Treated Systolic BP	N/A	-6.432	N/A	N/A
9	ln Untreated Systolic BP (mm Hg)	1.957	27.820	1.764	1.809
10	ln Age × ln Untreated Systolic BP	N/A	-6.087	N/A	N/A
11	Current Smoker (1=Yes, 0=No)	7.574	0.691	7.837	0.549
12	ln Age × Current Smoker	-1.665	N/A	-1.795	N/A
13	Diabetes (1=Yes, 0=No)	0.661	0.874	0.658	0.645
A	Baseline Survival	0.9665	0.9533	0.9144	0.8954
B	Individual Sum = $\sum(\text{coefficient} * \text{parameter})$	For each individual patient, individual sum is summation of product of each parameter and its corresponding coefficient for that sex-race group for all parameters listed above (#1 -#13). Note: N/A indicates that the specific coefficient is not available thus the corresponding parameter will not be included in calculation.			
C	Population Mean	-29.18	86.61	61.18	19.54
D	Pooled Cohort Risk Score	$ \begin{aligned} &= B - C \\ &= \text{Individual Sum} - \text{Population Mean} \end{aligned} $			
E	Pooled Cohort Risk = Estimated probability of a first hard ASCVD event within 10 years	$ \begin{aligned} &= 1 - A^{\wedge} \exp(B-C), \text{ ie,} \\ &= 1 - \text{Baseline Survival}^{\wedge} \exp(\text{Individual Sum} - \text{Population Mean}) \end{aligned} $			

ASCVD = atherosclerotic cardiovascular disease; BP = blood pressure; HDL-C = high-density lipoprotein cholesterol; ln = natural logarithm. Age is the actual age when the lab parameters are collected for the visit. Total Cholesterol and HDL-C, Systolic BP are assessed at a same visit when risk score are to be reported, where total cholesterol and HDL-C should be obtained on the same day. Smoker, and diagnosis of Diabetes are collected at Screening/Baseline on the page of Medical History. Status of hypertension treatment is determined based on prior and concomitant medications taken at baseline of the BD Phase for analysis for the visits in BD Phase, and on the date when the blood pressure is collected for the visit analyzed in the OLE Phase. Round Pooled Cohort Risk Score to 0.001.

Mayo Risk Score:

Mayo Risk Score $R = 0.03 \text{ Age (years)} + 0.54 \text{ Ln total bilirubin (mg/dL)} + 0.54 \text{ Ln AST (U/L)} + 1.24 \text{ variceal bleeding (0/1)} - 0.84 \text{ albumin (g/dL)}$.

Keep 2 decimal places. The lab parameters need to be measured from the same blood draw. Age should be the actual age at the date when lab values are taken. Status of variceal bleeding should also be decided on the lab date. If a subject has a history or new onset of variceal bleeding, the variceal bleeding variable will be set to 1 and carried over for future visits; otherwise 0.

5D-Itch Score:

5D-Itch contains a total of 5 questions with each ranging from 1 to 5. It includes 16 potential locations of itch, including 15 body part items and one point of contact with clothing or bandages. Single-item domain scores (duration, degree and direction) are equal to the value indicated below the response choice (range 1–5). The score for the disability domain is achieved by taking the highest score on any of the four items (sleep, leisure/social, housework/errands, and work/school). For the distribution domain, the number of affected body parts is tallied (potential sum 0 – 16, where body parts with missing responses are considered not affected and assigned a value of zero for summation) and the sum is sorted into five scoring bins: sum of 0 – 2 = score of 1, sum of 3 – 5 = score of 2, sum of 6 – 10 = score of 3, sum of 11 – 13 = score of 4, and sum of 14 – 16 = score of 5. The scores of each of the five domains are achieved separately. For subjects who have entered into OLE phase, the missing value on OLE day 1 for a domain is imputed using the corresponding last non-missing value in BD phase. The 5D-Itch total score is then the summation of the five domain scores. 5D-Itch scores can potentially range between 5 (no pruritus) and 25 (most severe pruritus) {[Elman et al 2010](#)}.

PBC-40 (for PSC Subjects):

PBC-40 scores are calculated using subject responses to 40 questions in the questionnaire. There are a total of 6 domains in the following across the 40 questions.

- Fatigue
- Emotion
- Social function
- Cognitive function
- General symptoms
- Itching

Analysis is by domain, with the scoring explained in the coded-PBC-40. Data should be considered by domain rather than in terms of a cumulative PBC-40 score. If data are missing from a domain (typically missed or duplicated answers) the whole domain should be discarded if $\geq 50\%$ of items are missing. If $> 50\%$ of responses are present then the median value for the completed items in the domain should be ascribed to the missing item {[Jacoby et al 2005](#)}.

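### Appendix 3 scores Pooled Cohort risk at actual age with no age range, and the printed White or Other female equation makes risk fall with age in young women

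*SAP*

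**What the plan says.** SAP Appendix 3 (Programming Specifications, Pooled Cohort Risk Score) prints four sex-by-race columns of coefficients. The score is the individual sum minus the population mean (row D), and the 10-year risk is 1 minus baseline survival raised to exp(score) (row E). On age it says: "Age is the actual age when the lab parameters are collected for the visit". It gives no lower or upper age and no rule for setting the score to missing outside a range. Smoking and diabetes status are taken from screening/baseline. The score is rounded to 0.001.

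Only the White or Other female column has a squared term in ln age. Its age terms read "ln Age (y) -29.799", "ln Age, Squared 4.884", "ln Age × ln Total Cholesterol -3.114", "ln Age × ln HDL-C 3.149" and "ln Age × Current Smoker -1.665", with "Baseline Survival 0.9665".

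Tables 3-2 and 3-5 (Section 3.8.2) window the score at visits of the blinded phase and of the open-label extension (OLE). Section 3.8.2 leaves it out of the long-term mapping. It also says that not every windowed visit of a derived risk score will be presented, and refers to Sections 6.1.1, 6.2.1 and 6.3.1 for those that will. That text is blacked out.

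**The concern.** A positive squared term with a negative linear term gives a curve with a minimum. If the minimum falls at an age that trial subjects can have, younger women on the left-hand branch are assigned more cardiovascular risk than somewhat older women with the same lipids, blood pressure and smoking status. Because age is re-entered at each visit, their score also drifts down during follow-up with nothing else changing.

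Two outputs are at stake: the level of the score, at baseline and afterwards, and its change during the OLE. OLE groups 5 to 8 (Section 3.2) all receive active drug, so no concurrent control shows how much of a fall is due to ageing. The SAP does not state the entry ages. The Appendix 1 schedule does provide pregnancy tests for women of childbearing potential, so women this young are foreseeable.

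**Working it through.** The plan has no worked example of this score, so there is no stated figure to reproduce.

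**Inputs.** The White or Other female column of Appendix 3: the terms quoted above, plus ln total cholesterol (TC) 13.540, ln HDL-C -13.578, ln untreated systolic pressure (SBP) 1.957, current smoker 7.574, and population mean -29.18. Assumed for illustration, because the SAP has no such data: TC 200 mg/dL, HDL-C 50 mg/dL, untreated SBP 115 mmHg, no diabetes. Two further lipid profiles are used for the turning age.

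**Turning age.** With L = ln age, the slope of the score in L is

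-29.799 + 2 × 4.884 L - 3.114 ln TC + 3.149 ln HDL-C - 1.665 × smoker.

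Setting this to zero gives

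age = exp[(29.799 + 3.114 ln TC - 3.149 ln HDL-C + 1.665 × smoker) / 9.768].

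The squared coefficient is positive, so this is a minimum. SBP and diabetes do not enter. For TC 200 and HDL-C 50: exp(33.979 / 9.768) = 32.4 years (non-smoker) and exp(35.644 / 9.768) = 38.4 years (smoker).

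| TC / HDL-C (mg/dL) | Non-smoker | Smoker |
|---|---|---|
| 200 / 50 | 32.4 | 38.4 |
| 240 / 45 | 35.5 | 42.1 |
| 180 / 70 | 28.1 | 33.3 |

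**Levels at TC 200, HDL-C 50, SBP 115.** The terms free of age sum to 13.540 ln 200 - 13.578 ln 50 + 1.957 ln 115 + 29.18 = 57.088. So

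score = 57.088 - 33.979 L + 4.884 L² + smoker × (7.574 - 1.665 L).

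For a non-smoker aged 25, L = 3.2189. The score is 57.088 - 109.374 + 50.604 = -1.683 after rounding, and risk = 1 - 0.9665^exp(-1.683) = 0.63%. In the same way:

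| Age | Non-smoker | Smoker |
|---|---|---|
| 20 | 1.41% | 17.2% |
| 25 | 0.63% | 5.6% |
| 30 | 0.47% | 3.1% |
| 38 | 0.51% | 2.3% |
| 50 | 1.13% | 3.2% |

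**Change from ageing alone**, all else fixed. 96 weeks is 672 days, or 1.84 years; 12 weeks is 84 days, or 0.23 years.

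| Start age | Smoker | Score change, 12 weeks | Score change, 96 weeks | Risk over 96 weeks |
|---|---|---|---|---|
| 25 | no | -0.023 | -0.156 | 0.63% to 0.54% |
| 25 | yes | -0.038 | -0.274 | 5.6% to 4.3% |
| 30 | no | -0.005 | -0.028 | 0.47% to 0.46% |
| 30 | yes | -0.018 | -0.127 | 3.1% to 2.8% |
| 35 | no | +0.005 | +0.051 | 0.47% to 0.49% |

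For scale, the SBP coefficient of 1.957 makes -0.156 equal to a fall in SBP from 115 to 115 × exp(-0.156 / 1.957) = 106 mmHg, and -0.274 equal to a fall to 100 mmHg.

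**Other columns.** The White or Other male slope in ln age was positive at every value tried (TC 150 to 280, HDL-C 30 to 80, smoker or not): +1.55 to +6.75. The African American male slope is a constant +2.469. The African American female slope was positive except at one extreme corner (treated SBP 170 with HDL-C 30). The reversal is in practice confined to White or Other women.

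**The case against.** The strongest reply is that the visible text is incomplete. Section 6 is blacked out, and it or the protocol may limit the ages scored, the visits shown, or whether change is analysed at all. That stands, and it limits the point to what Appendix 3 says. But Appendix 3 is the rule the programmer follows, and as written it scores every age.

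The second reply is size. The large risks belong to young smokers. A non-smoker aged 25 loses 0.09 percentage points over 96 weeks, one aged 30 about 0.01, and one aged 35 gains. Over the 12 blinded weeks the drift at age 25 is -0.02 to -0.04 score units and follows the same rule in every arm. A reader might infer that the blinded comparison is materially distorted; the figures do not support that.

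A reader might also infer that one or two young smokers would dominate an arm mean in groups of 10 to 20. That does not hold in general, because the score in row D is on the log scale. At the same lipids and SBP 115 the White or Other male column gives

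12.344 L + 11.853 ln TC - 2.664 L ln TC - 7.990 ln HDL-C + 1.769 L ln HDL-C + 1.764 ln SBP + smoker × (7.837 - 1.795 L) - 61.18,

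which is 0.31 for a smoker aged 60 and -3.75 for a non-smoker aged 30. A female smoker aged 25 scores 0.53, within the ordinary spread; one aged 20, at 1.71, does stand out. Section 3 also calls for medians and quartiles.

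Finally, an age limit alone need not remove the reversal, because the turning age reaches 42.1 years in one smoker profile. This is why the remedy needs a second element.

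**Conclusion.** The point holds as a correction to a programming rule for one exploratory score. Followed as printed, Appendix 3 gives White or Other women a risk that falls with age below about 28 to 36 years (non-smokers) or 33 to 42 years (smokers). That makes levels in young women misleading: at the illustrative values a non-smoker of 20 is rated above one of 50. It also builds a downward drift into uncontrolled OLE change, -0.156 to -0.274 score units over 96 weeks from age 25, against a reporting precision of 0.001.

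The turning ages and drifts follow from the printed coefficients, given the assumed lipids and smoking status; the levels also depend on the assumed SBP. The effect on group summaries cannot be stated, because the SAP gives neither entry ages nor the number of young White or Other women. The primary safety objective is not affected.

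**What to change.** In Appendix 3:

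- When computing change from baseline, hold age at its baseline value for the phase being analysed. Smoking and diabetes are already fixed, so change then reflects only lipids, blood pressure and hypertension-treatment status.
- Calculate the score only for subjects within the age range for which the cited guideline gives the equations, with the bounds taken from that reference. Set the score to missing outside that range and report the number excluded by group.

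If Section 6 already restricts age, repeat the restriction in Appendix 3. The first change removes the ageing drift but not the misleading levels; the second addresses the levels. The cost is a few lines of specification and fewer subjects contributing to one exploratory score. The loss cannot be sized from the SAP, and it would also remove men and African American women outside the range.
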